## V. PROTOCOL

### A. STUDY GROUPS

We will randomize up to 200 children, 1 month (30 days) -18 months of age, who meet all inclusion criteria and do not have any of the exclusion criteria. Children will be randomized in a 1:1 manner to one of the 2 treatment arms (azithromycin or placebo).

**PATIENT IDENTIFICATION AND ENROLLMENT:** Recruitment and enrollment will be conducted over 3 consecutive RSV seasons: starting with the 2016-2017 RSV season (usually November- April) and concluding during the 2018-2019 RSV season. The SLCH census list will be reviewed daily (during the RSV season) for all potential admissions with RSV bronchiolitis. Furthermore, all positive RSV FA/PCR from the virology lab at SLCH will be investigated to assess eligibility for this study. Based on these lists, we will pre-screen the medical records for study inclusion/exclusion criteria. If there are no apparent exclusions, the study coordinator will approach the child, after obtaining permission from the physician in charge of the child's care, to determine eligibility.

Estimates of annual enrolment for each RSV season were based on the institution's (SLCH) historical data. Over seven years in two prior studies (the RBEL cohorts), the average enrolment rate at SLCH was 65-70 subjects per RSV season. The range of newly enrolled subjects during the same period varied between 35 and 100.

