### Primary outcome analysis:

The initial analytic strategy will be a log-rank test, which compares the Kaplan Meier survival curves describing the time to the third episode of wheezing.

Then, the primary analysis of the primary endpoint will be conducted using a stepwise Cox regression model that would include 2 covariates: race and parental history of asthma. These 2 covariates were significant predictors of childhood asthma development following severe RSV bronchiolitis in our RBEL cohort. If the proportional hazards assumption is violated, we will follow the recommendations of Allison and will address the problem by including in the model an interaction term between time and the variable that violates the proportional hazards assumption.

At the next step, we will conduct multivariate analysis that will include other covariates that may be associated with the primary outcome. Chi square tests, t-tests, and potentially Wilcoxon's test will be used to compare all non-time dependent covariates listed below\* across groups in order to identify variables that should be included in subsequent multivariate models. Those fixed-time covariates that yield at least some suggestion of a between-group difference ( $p < 0.1$ ) will then be included in a stepwise Cox regression analysis along with all of the time dependent covariates (e.g., pet exposure). Additional analyses will include the use of an Anderson-Gill model in which wheezing episodes are treated as recurrent events when compared between groups. In Cox models that do not contain time dependent covariates, we will evaluate the proportional hazards assumption by assessing the parallelism of the log-log plots and using martingale residuals and the method of Lin, and Ying. The Cox models which contain time-dependent covariates will be tested using Schoenfeld residuals.

The key statistic to be generated by the Cox regression analyses, for primary outcome reporting, will be covariate adjusted hazard rate ratios that compare the RW hazard rate in the azithromycin group with the corresponding hazard rate in the control group. Ninety-five percent confidence bounds will be generated for all calculated hazard rate ratios.

Finally, we will explore for potential interactions between study treatment assignment and pre-specified covariates to evaluate whether these covariates are predictors of response to azithromycin therapy:

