### **B.1. Clinical outcome:**

Power calculations were performed using the program Power and Precision, Version 4. They account for recruitment of patients over 3 consecutive RSV seasons (~5 months per year) with a follow up period of 18-48 months (**Figure 1: Study Design**). Our power computations are based on an evaluation of the four year survival and hazard curves generated by 190 participants of the RBEL I cohort who share the same characteristics as the controls in this proposed research, and hence used to estimate the RW rate in the control group. The survival pattern observed in our randomized pilot study (APW-RSV) was utilized to estimate the effect of the intervention. The RBEL survival curves show a low placebo group hazard rate (HR) of about 2% during the first three months after hospitalization. This HR increases steadily to about 5% per month at the end of the first year. After that, HRs decrease steadily to 3% per month by the end of year 2 to a steady monthly rate of 2% during year 3, and 1% during year 4. These assumptions yield a four-year hazard rate of 71.6%, nearly identical to the actual rate of 70.4% observed in RBEL I. We used the HR as described as the basis for the placebo group in our power computation. These projected hazard rates yield a four-year hazard rate of 55.1%. Thus, the power computations summarized below represents hazard rates of 71.6% in the placebo group and 55.1% in the azithromycin group over the follow-up period. Based on the parameters described above, two-sided tests at the 0.05 level of significance, and assuming a dropout rate of 20%, **power computations yield a requirement of 94 randomized subjects per group for a power of 0.9, and 70 per group for a power of 0.8.** Based on these considerations, we will randomize a total of up to 200 subjects or 94 per group, numbers that yield the target power of 0.9. In evaluating these computations, it is important to note that we have assumed a hazard ratio during the first 18 months of at least 2. While this is a substantial hazard ratio, we emphasize in the next paragraph that our pilot randomized trial with one year of follow-up yielded a hazard ratio of 0.34 (comparing azithromycin with placebo) meaning that the observed risk associated with placebo compared to azithromycin was nearly 3.

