**We strongly believe that these power computations yield an adequate and indeed conservative sample size for the following reasons:** First the excellent target power of 0.9 and the need for only 70 subjects per group to achieve a power of 0.8 suggest that we will still have adequate power if recruitment is slower than it has been in the past. Second, the assumed HR ratios ( $55.1/71.6 = 0.77$ ) are substantially greater than the 0.34 observed in our APW-RSV pilot study. Although this large hazard rate ratio difference between those projected in this study (0.77) and the pilot study (0.34) are mitigated somewhat by the fact that the pilot study follow-up period was only one year, we have based our computations on hazard rate ratios that are closer to 1 than in the pilot study, even during the first year. Therefore, we are powered to detect between group differences that are smaller than were observed in our pilot study. Third, we assumed a HR of 1 during years 3-4. This is a very conservative approach as we believe that prevention of inflammatory damage to the airway during the acute RSV bronchiolitis will result in ongoing preventative effect for wheezing prevention during childhood

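### If treatment fails the proportional-hazards check, the Cox model called primary no longer has one treatment effect, and the plan names no contrast or p-value to decide the trial

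*Combined protocol and SAP*

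**What the plan says.** Section VII.A gives two answers on what is primary. Under General approach, the primary analysis is an intention-to-treat comparison of Kaplan–Meier curves, and a Cox model then estimates the size of the effect. Under Primary outcome analysis, the log-rank test is only the initial step, and the primary analysis is a stepwise Cox model with race and parental asthma as covariates. Sections II.F.1 and V.F.1 also measure the primary outcome with a Cox model, and Appendix 2 (Analysis plan) speaks of keeping the pre-specified Cox model as primary.

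If proportional hazards (PH) fails in that model, the response is "including in the model an interaction term between time and the variable that violates the proportional hazards assumption". PH is to be judged from log-log plots and martingale residuals (the Lin–Wei–Ying method) when the model has no time-dependent covariates, and from Schoenfeld residuals when it has. The key reported statistic is the adjusted hazard ratio of azithromycin against control, with 95% bounds.

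Section VII.B.1 sets out the planned effect for placebo relative to azithromycin: "we have assumed a hazard ratio during the first 18 months of at least 2", and later "Third, we assumed a HR of 1 during years 3-4". The error level given there is "two-sided tests at the 0.05 level of significance".

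The plan does not give a threshold for declaring a violation, the function of time, how time is centred, or which contrast decides the trial once the interaction is in the model. The reference number attached to the rule (15) leads in Section IX to a report on asthma and allergy after RSV bronchiolitis, so the details cannot be traced from there.

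**The concern.** The form of the model called primary depends on a diagnostic run on the same data, and the sponsor's own planning assumption makes treatment a candidate to fail it. With a treatment-by-time term the hazard ratio becomes a curve. The treatment coefficient is then the log hazard ratio where the time variable equals zero, which for uncentred time is the very start of follow-up.

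Two things are at stake. First, in the scenario the trial was planned for, there may be no defined primary estimate or p-value. Second, whoever picks the contrast after seeing the diagnostic also picks the type I error and may report an estimate from the edge of the data.

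**Working it through.** **Inputs from Section VII.B.1 and Section VII.A.** Two-sided 5%; "requirement of 94 randomized subjects per group for a power of 0.9" (70 for 0.8); 1:1 allocation; 20% dropout; four-year event proportions 71.6% and 55.1%; placebo hazard about 2% per month for three months, rising to 5% at month 12, falling to 3% at month 24, then 2% in year 3 and 1% in year 4; follow-up up to 48, up to 36 and at least 18 months by season.

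**Assumptions.** Hazards interpolated linearly; exponential dropout; equal season sizes; follow-up of 42–48, 30–36 and 18–24 months; no covariates. The plan gives no treatment hazard ratio for months 18–24, so two patterns are used: 0.5 to month 18 then 1, and 0.5 to month 24 then 1.

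**1. The plan's own figure.** Freedman's formula with HR 0.5:

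- Events = (1.960 + 1.282)² × ((1 + 0.5)/(1 − 0.5))² = 10.51 × 9 = 94.6.
- Mean event proportion = (0.716 + 0.551)/2 = 0.6335.
- Per group: 94.6/0.6335/2 = 74.6; divided by 0.8 = 93.3, so 94.
- For power 0.8: 70.6 events, 69.7, so 70.

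Both stated sizes are reproduced, but only with a constant hazard ratio of 0.5. That is an arithmetic match, not proof of how the program was run. The text describes an effect that is not constant.

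**2. Why the choice of contrast matters.** The interaction model is log HR(t) = b0 + b1·t. Under the null, the z-statistics for b0 and b1 correlate at −0.84. A trial flagged at 5% has an average |z| for b1 of 0.05845/0.025 = 2.34, which implies a |z| for b0 of about 0.84 × 2.34 = 1.96. About half of flagged null trials therefore reject on b0 (simulated: 48–50%). Overall:

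- Schoenfeld screen: 0.949 × 0.047 + 0.051 × 0.481 = 0.069.
- Lin–Wei–Ying screen: 0.962 × 0.047 + 0.038 × 0.348 = 0.058 (simulated 0.059).

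Near the middle of the event times, log HR(t) is almost uncorrelated with the slope, so selecting on the slope does little harm there.

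**3. Simulated type I error, 94 per arm** (60,000 null trials, standard error about 0.1 point; 0.15–0.2 point for the log-time, joint-test and looser-screen rows)

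| Decision rule | Type I error |
|---|---|
| Log-rank, fixed in advance | 4.9% |
| Single Cox HR, fixed in advance | 4.7% |
| Two-stage, time-zero coefficient, 5% Lin–Wei–Ying screen | 5.9% |
| Same, 5% Wald / Schoenfeld screen | 6.8% / 6.9% |
| Same, log time (HR at 1 month) | 7.0% |
| Same, 10% or 20% screen | 7.4–8.0% |
| Two-stage, joint 2-df test, 5% screen | 6.3–6.5% |
| Two-stage, HR at 24 months, 5% Wald or Schoenfeld screen | 6.6–6.7% |
| Two-stage, HR at 12 months or mean event time | 4.7–4.8% |

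**4. Under the planned effect, 94 per arm** (8,000 trials per pattern, three 5% screens)

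| | 0.5 to month 18, then 1 | 0.5 to month 24, then 1 |
|---|---|---|
| Treatment flagged | 20.1–24.5% | 7.3–13.7% |
| Flagged trials: median HR(0), true 0.5 | 0.25 | 0.23 |
| Flagged trials: median HR(12 months), true 0.5 | 0.53–0.54 | 0.47–0.48 |
| Flagged trials: median HR(36 months), true 1 | 2.39–2.45 | 1.98–2.06 |
| Rejection rate: fixed log-rank / fixed Cox | 67.4% / 66.8% | 82.4% / 82.0% |
| Rejection rate: two-stage, time zero | 72.7–74.6% | 82.7–84.2% |
| Rejection rate: two-stage, 24 months | 51.0–54.1% | 71.1–76.5% |

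Time zero is at the edge of the data: about 3–4 events fall in month 1 and 8–10% of events before month 3, with a median event time of about 11–13 months.

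**The case against.** The best defence starts from the General approach paragraph. There the Kaplan–Meier comparison is primary, the log-rank test carries no PH condition, and the Cox model only estimates. On that reading type I error stays near 4.9%. This is a fair reading of that paragraph, but not of the plan: the Primary outcome analysis text, Sections II.F.1 and V.F.1, and Appendix 2 all tie the primary result to Cox. It also leaves open which hazard ratio is the key reported statistic once treatment varies with time.

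A reader might infer that the rule by itself raises type I error to about 7%, or that the plan replaces the treatment effect with a time-zero hazard ratio. The documents do not support either. They never mention a time-zero ratio, and reporting hazard ratios in the plural is compatible with several time points. The 7% figure needs treatment to be the violating variable, a 5% Wald or Schoenfeld screen, uncentred time, and the time-zero coefficient as the deciding test. The method named for this model gives 5.9%, and reading the same model at 12 months gives no inflation. Nor is the estimate exaggerated at every time: the 12-month medians are close to the truth.

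Two further points stand. The rule also covers race and parental asthma, where a time interaction leaves one treatment hazard ratio intact, and it is not shown that treatment is the variable most likely to fail. A treatment-by-time term is also a recognised response to non-proportionality, so banning it outright would be a matter of preference.

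**Conclusion.** The concern holds as a defect in how the primary result is defined. The plan states a two-stage rule, does not exempt treatment, expects non-proportional treatment hazards, and does not say what decides the trial when the rule applies to treatment. Under the planned effect and an assumed 5% screen, that happens in about 7–25% of trials.

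The size of the error is a range, about 4.7% to 8.0%, set by choices the plan leaves open. A test fixed in advance holds 4.7–4.9%. In flagged trials a linear-time model can roughly halve the early hazard ratio at time zero and suggest late harm at 36 months that is not there.

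These figures rest on the simulation assumptions listed above, notably the dropout timing, the absence of covariates and the two patterns for months 18–24. The direction of the result follows from the correlation between the two coefficients; the exact percentages do not carry over to other settings.

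**What to change.** Reconcile the two parts of Section VII.A by naming one primary test, either the log-rank test or the single pre-specified Cox model, and state that it decides the trial whatever the PH diagnostics show. Bring Sections II.F.1 and V.F.1 and Appendix 2 into line.

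If PH fails for treatment, keep that p-value and describe the Cox hazard ratio as an average over follow-up. As description only, add piecewise hazard ratios (0–18 months and later), a restricted-mean difference, or a treatment-by-time model with its time function and reading times stated in advance. Time interactions for race or parental asthma may stay in the model.

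The cost is one paragraph of SAP text, with no change to enrolment, data collection or care. Compared with a two-stage rule read at time zero, a fixed Cox test gives up between 0.7 points (82.7 − 82.0) and 7.8 points (74.6 − 66.8) of nominal power. That comparison is not like for like, because the two-stage rule runs at 5.9–6.9% type I error under the same screens.

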- a. Demographic: Sex, age, race.
- b. Baseline asthma/allergy phenotypic characteristics: Personal history of eczema, parental history of asthma, peripheral eosinophil count on enrolment.
- c. Environmental phenotypic characteristics: second hand smoking, pet exposure.
- d. Acute bronchiolitis characteristics: Duration of respiratory symptoms before enrolment, and the presence of co-infection with other respiratory viruses during the RSV bronchiolitis (e.g. rhinovirus).

\*The following covariates will be compared between the groups and would be considered to be included in the Cox models:

- a. Age at enrollment (months)
- b. Gender
- c. Race
- d. Birth weight
- e. Length of pregnancy (wks)
- f. Maternal smoking status during pregnancy
- g. Breast feeding status at the time of enrollment

- h. Tobacco smoke exposure (at the time of enrollment and during f/u visits)
- i. Pet exposure (at the time of enrollment and during f/u visits)
- j. History of eczema
- k. Parental history of asthma
- l. Duration of respiratory symptoms prior to randomization
- m. Duration of hospitalization (hours: measured from the time of the Emergency Room visit that triggered the admission and until time of discharge)
- n. Lowest O2 saturation recorded on room air
- o. Antibiotics use during the acute hospitalization. Antibiotic use during the follow up period will be measured as one of the secondary outcomes.
- p. Co-infection with other respiratory virus on enrollment (mainly Rhinovirus)
- q. Complete compliance with study medication (defined as >80% compliance)
- r. Antipyretic (acetaminophen and Ibuprofen) use during the initial RSV bronchiolitis
- s. Day care attendance
- t. Number of siblings in the house
- u. Eosinophil count at enrollment

**Censoring considerations:** All subjects will be censored at the time of the last contact with the subject confirms that they had not experienced the outcome measure. This applies whether the subject is a dropout or has remained on study until the end.

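### The follow-on multivariable Cox model admits baseline covariates only when the randomised arms happen to differ on them (p<0.1), so balanced predictors of wheeze are left out

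*Combined protocol and SAP*

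**What the plan says.** Section VII.A, Primary outcome analysis, sets out three steps for the time to the third wheezing episode.

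1. A log-rank test.
2. A Cox model with race and parental history of asthma. This is called the primary analysis of the primary endpoint. The two covariates were chosen because they predicted asthma in the sponsor's earlier RBEL cohort.
3. A multivariable Cox model meant to bring in further covariates that may be related to the outcome. Chi-square, t- or Wilcoxon tests compare the groups on each fixed covariate, and the stated purpose of these tests is "in order to identify variables that should be included in subsequent multivariate models". The entry rule that the plan then gives has its threshold at p<0.1: "Those fixed-time covariates that yield at least some suggestion of a between-group difference" go into a stepwise Cox model together with all time-dependent covariates.

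The list that follows (items a to u) is introduced in the same terms: the "covariates will be compared between the groups and would be considered to be included in the Cox models". Race and parental asthma are on that list too (items c and k), and nothing says that they stay in the step 3 model if balanced.

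The key statistic "for primary outcome reporting, will be covariate adjusted hazard rate ratios". The text does not say which of the Cox models supplies it. Under Sensitivity analyses, the plan adds a LASSO selection over the fixed covariates.

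**The concern.** The aim of step 3 and its entry rule do not match. The aim is to include covariates that bear on wheeze. The rule asks only whether the arms differ on them. I read the groups as the treatment arms, which is the plain sense of the text.

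Allocation is randomised 1:1, so a difference between arms on a true baseline item is chance and says nothing about whether that item predicts wheeze. Adjustment sharpens a time-to-event comparison when the covariate predicts the outcome, whether or not it is balanced. The screen shuts out any predictor that is balanced at the 0.1 level. It also leaves the covariate set to be settled by chance, after a comparison that needs the group labels.

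At stake are the precision of the step 3 hazard ratio and the clarity of what will be reported, because the plan does not exclude this model as the source of the adjusted hazard ratio.

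**Working it through.** **1. The plan's own power figure.** Section VII.B.1 uses "two-sided tests at the 0.05 level of significance, and assuming a dropout rate of 20" percent and reports "a requirement of 94 randomized subjects per group for a power of 0.9, and 70 per group for a power of 0.8", from "hazard rates of 71.6% in the placebo group and 55.1% in the azithromycin group over the follow-up period". It also says: "we have assumed a hazard ratio during the first 18 months of at least 2". The azithromycin monthly hazards are not given, so the figure has no unique reproduction. I interpolated the placebo hazard between the stated points and scaled it to 71.6%. Follow-up was 43-48, 31-36 and 18-24 months by season, with exponential dropout of 20% over 48 months, and the azithromycin risk was held at 55.1% with a hazard ratio of 1 in years 3-4.

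- Azithromycin/placebo hazard ratio 0.50 to month 18 and 0.43 in months 18-24: power 0.838 with 94 per group, 0.720 with 70.
- 0.40 to month 18 and 0.74 in months 18-24: power 0.897 and 0.795.

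The second case still fits a ratio of at least 2, so the stated figure is attainable. It does not depend on the covariate screen.

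**2. How many candidates are baseline items.** The list has 21 items.

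- Remove race and parental asthma: 21 - 2 = 19.
- Remove the three time-dependent items. The plan gives the number but does not name them; I take them as tobacco smoke, pets and day care: 19 - 3 = 16.
- Remove compliance and duration of hospitalisation, which accrue after randomisation: 16 - 2 = 14.
- Remove in-hospital antibiotics, antipyretics and lowest oxygen saturation, which can accrue after randomisation: 14 - 3 = 11.

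The 11 are age, sex, birth weight, length of pregnancy, maternal smoking in pregnancy, breast feeding, eczema, symptom duration before randomisation, viral co-infection, siblings and eosinophils.

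**3. What the screen does under randomisation.** For k independent baseline items, the expected number passing is 0.1k and the chance of at least one is 1 - 0.9^k.

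| k | Expected picks | At least one |
|---|---|---|
| 11 | 1.1 | 1 - 0.9^11 = 69% |
| 14 | 1.4 | 1 - 0.9^14 = 77% |
| 16 | 1.6 | 1 - 0.9^16 = 81% |

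A given predictor fails the screen with probability 1 - 0.1 = 90%.

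**4. Power.** I simulated Cox models with 94 per arm, the plan's placebo hazard, the follow-up and dropout of step 1, and a treatment hazard ratio constant over time (6,000 trials per power cell). The following are my assumptions: two always-included binary covariates with hazard ratio 1.5 each, and 14 independent candidates, of which 3 are prognostic with the strength shown.

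| Treatment HR | Model | HR per SD 1.0 | 1.2 | 1.4 | 1.6 |
|---|---|---|---|---|---|
| 0.5 | Two covariates | 0.896 | 0.876 | 0.835 | 0.777 |
| 0.5 | Plus screened items | 0.887 | 0.869 | 0.833 | 0.785 |
| 0.5 | Screen, then stepwise | 0.895 | 0.876 | 0.841 | 0.794 |
| 0.5 | Plus 3 prognostic items, fixed | 0.892 | 0.894 | 0.896 | 0.901 |
| 0.6 | Two covariates | 0.695 | 0.659 | 0.611 | 0.532 |
| 0.6 | Plus screened items | 0.684 | 0.648 | 0.609 | 0.533 |
| 0.6 | Screen, then stepwise | 0.695 | 0.660 | 0.621 | 0.545 |
| 0.6 | Plus 3 prognostic items, fixed | 0.692 | 0.685 | 0.695 | 0.694 |

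Against the two-covariate model, the screen moves power by between -1.1 points (0.684 - 0.695) and +1.7 points (0.794 - 0.777). Fixed prognostic adjustment moves it by about 0 with no prognosis. It gains 1.8 to 2.6 points at 1.2 per SD, and 12.4 to 16.2 points at 1.6. On average 0.30 of the 3 prognostic items passed the screen, as the 10% rule predicts. With no treatment effect, rejection rates for the screened models lay between 0.043 and 0.059.

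**5. A second simulation with a different effect shape.** This used 188 children, a placebo/azithromycin ratio of 2 to month 24, 16 candidates and 1,200 trials per case. Power is for two covariates / screen then stepwise / fixed prognostic items:

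- 2 predictors at HR 1.3 per SD: 0.786 / 0.788 / 0.821.
- 4 predictors at 1.3: 0.758 / 0.760 / 0.837.
- 4 predictors at 1.5: 0.695 / 0.697 / 0.858.

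The pattern is the same.

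**The case against.** The strongest reply is that the quoted rule does not govern the primary analysis. The model given that name has two covariates, chosen for prognosis, and it already yields an adjusted hazard ratio. This stands. A reader might infer that the headline treatment effect is adjusted for covariates picked on imbalance. The documents do not support that. They only fail to say which Cox model is reported.

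Other replies also have force.

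- **The stepwise stage uses the outcome.** True: an admitted item must also relate to wheeze to stay. But stepwise selection works on what the screen let through and cannot restore what it excluded.
- **The LASSO can bring in balanced predictors.** It can, but it is placed under sensitivity analyses and leaves the rule in step 3 unchanged.
- **No harm relative to the plan is shown.** Correct. A reader might infer inflated false positives, or power below the planned 0.90 because of the screen. Neither follows: the null rejection rate is near nominal and the screened model performs like the two-covariate model. What is lost is a gain that could have been had.
- **The gain rests on assumed prognosis.** Correct. No document gives prognostic strengths for the other listed items.
- **Part of the fall in power in the simulations is a modelling artefact.** The plan's hazards are cohort averages, so adding predictors on top of them changes the average curve. With the average curves held fixed, screened power stayed at 0.80 to 0.82 in the three cases of the second simulation. The gap to prognostic adjustment was 3, 5 and 11 points with the effect lasting to month 24, and 6 to 16 points with it ending at month 18. A gap remains.

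**Conclusion.** The point holds for the follow-on multivariable model only. Its entry rule selects on chance imbalance, contrary to that step's stated purpose. The 10% pass rate follows from the rule and from randomisation. The counts (1.1 to 1.6 chance picks, at least one in 69% to 81% of trials) assume independent items, which is not exact; birth weight and length of pregnancy, for example, are likely to be correlated.

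The screen gains essentially no power over the two-covariate model and does not disturb type I error. The forgone gain is about 0 if the other items do not predict wheeze, 2 to 3 points at a hazard ratio of 1.2 per SD, and up to about 16 points if prognosis is strong. Those strengths are assumptions. This is a matter of precision and of a covariate set left to chance, not of validity. It is worth correcting because the remedy is cheap and the plan leaves open which model is reported.

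**What to change.** In section VII.A, Primary outcome analysis:

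- Delete the between-arm p<0.1 screen.
- Before unblinding, fix a short list of true baseline covariates from items a to u. Choose them by their association with recurrent wheeze in RBEL, or in pooled trial data without treatment codes. This extends the reasoning already used for race and parental asthma.
- Enter that list whatever the baseline balance, with treatment, race and parental asthma forced in.
- Show baseline balance descriptively, without tests.
- State whether the two-covariate model or this pre-specified model supplies the reported adjusted hazard ratio.

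The cost is a change of wording in the analysis plan, one look at RBEL or pooled blinded data, and a few degrees of freedom. Sample size and trial conduct do not change.
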